## **1. PROBLEM STATEMENT**

Patients receiving maintenance hemodialysis (MHD) suffer from highly prevalent fatigue (60-97%) and anxiety (up to 90%), which severely impact their quality of life and treatment adherence. In Iraq, resource-limited settings and the impracticality of foot reflexology (due to lower limb edema and vascular access issues) necessitate safe, non-pharmacological nursing interventions. Hand Reflexology Massage (HRM) is a viable, safe, and cost-effective option, yet its efficacy in simultaneously reducing both fatigue and anxiety in Iraqi MHD patients lacks randomized controlled trial (RCT) evidence.

## **2. RESEARCH QUESTION**

How effective is HRM in reducing fatigue and anxiety levels in patients receiving MHD compared to usual care after eight sessions?

## **3. HYPOTHESES**

There is a statistically significant difference in fatigue and anxiety levels between hemodialysis patients receiving HRM plus usual care and those receiving usual care alone.

## **4. OBJECTIVES**

- Assess baseline fatigue and anxiety levels prior to HRM.
- Evaluate the effect of the HRM program on fatigue and anxiety post-intervention.
- Compare post-intervention changes between the intervention and control groups.
- Examine associations between socio-demographic/clinical characteristics and HRM effectiveness.

## **5. DEFINITION OF TERMS (Operational)**

- Hand Reflexology Massage (HRM): A 21-minute organized protocol applied by nurses to specific reflex zones on both hands (solar plexus, diaphragm, adrenal gland, kidney, pituitary gland, and heart) during dialysis sessions.
- Fatigue: Measured using the Arabic FACIT-Fatigue Scale (13 items, scored 0-52). Higher scores indicate lower fatigue levels and better quality of life.

- Anxiety: Measured using the Arabic Beck Anxiety Inventory (Ar-BAI) (21 items, scored 0-63). Scores are classified into minimal (0-7), mild (8-15), moderate (16-25), and severe (26-63) anxiety.

## 6. METHODOLOGY

- **Study Design:** Two-group parallel Randomized Controlled Trial (RCT) with a 1:1 allocation ratio.
- **Setting:** Hemodialysis units in Iraq.
- **Sample Size:** 70 adult patients receiving MHD (35 in the intervention group, 35 in the control group).
- **Intervention Group:** Received eight 21-minute HRM sessions over four weeks (two sessions per week) during routine hemodialysis, in addition to usual care.
- **Control Group:** Received usual care only (routine dialysis nursing care) without HRM.
- **Data Collection Time Points:**
  - T0: Baseline (before the first session).
  - T1: Mid-intervention (after the 4th session).
  - T2: Post-intervention (after the 8th session).

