## 7. STUDY INSTRUMENTS

1. Demographic and Clinical Characteristics Questionnaire (age, gender, education, income, duration of HD, etc.).
2. Arabic FACIT-Fatigue Scale (Version 4).
3. Arabic Beck Anxiety Inventory (Ar-BAI).

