## **9. STATISTICAL ANALYSIS PLAN**

- Normality Testing: Shapiro-Wilk test will be used to assess the normal distribution of continuous variables.
- Within-Group Comparisons: Parametric tests (e.g., Repeated Measures ANOVA) for normally distributed data, and non-parametric tests (e.g., Friedman test) for non-normal data across the three time points (T0, T1, T2).
- Between-Group Comparisons: Independent t-test or Mann-Whitney U test to compare post-intervention scores between the intervention and control groups.
- Multiple Comparisons: Bonferroni correction will be applied for post-hoc pairwise comparisons to control Type I error.
- Associations: Chi-square or Fisher's exact tests will be used to examine relationships between demographic/clinical characteristics and HRM effectiveness.
- Clinical Significance: Minimal Clinically Important Difference (MCID) will be calculated to determine the practical relevance of fatigue and anxiety score improvements. Analysis will be performed using SPSS.

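### More than one hemodialysis unit, but unit is not stated to enter the allocation and has no term in the between-arm test: a small, cheaply avoided loss of efficiency

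*Combined protocol and SAP*

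**What the plan says.** Section 6 (Methodology) gives the setting as "Hemodialysis units in Iraq": a plural, with no count and no patients per unit. The design is a "Two-group parallel Randomized Controlled Trial (RCT) with a 1:1 allocation ratio", with "70 adult patients receiving MHD (35 in the intervention group, 35 in the control group"). Nothing is said about sequence generation, blocking or strata, or about whether patients or whole units are randomised.

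Section 9 (Statistical Analysis Plan) specifies the between-arm comparison as "Independent t-test or Mann-Whitney U test to compare post-intervention scores between the intervention and control groups". It names no covariate, and neither unit nor clustering is mentioned anywhere in the analysis.

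Section 7 (Study Instruments) lists a "Demographic and Clinical Characteristics Questionnaire (age, gender, education, income, duration of HD, etc".). Unit is not named there, but the list is open-ended.

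**The concern.** Hemodialysis units can plausibly differ in case mix, staff and everyday nursing care. The last is the comparator here, and nurses also deliver the massage. Both outcomes are questionnaire scores (FACIT-Fatigue, 0-52; Ar-BAI, 0-63) that could vary by unit. A two-sample test that pools all 70 patients leaves any such variation in the error term.

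What follows depends on the allocation, on which the protocol is silent:

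- **Allocation blind to unit.** The arms may be spread unevenly over units by chance, and the treatment difference is estimated somewhat less precisely than it could be.
- **Allocation balanced within unit.** The estimate already benefits from the balance, but the plain test does not credit it, so the standard error is too large.

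With 35 patients per arm, precision is worth protecting where that costs almost nothing.

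**Working it through.** **Inputs from the documents.** 70 patients, 35 per arm; two-sample test on post-intervention scores; more than one unit.

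**Not in the documents, so assumed.** Number and size of units; share *r* of score variance due to unit; alpha, sidedness, power, SD and target difference. The figure of 70 therefore cannot be reproduced. Back-solved, 35 per arm gives 80% power for a standardised difference d = 0.67 at two-sided alpha 0.05, and this is the reference below.

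**1. Upper bound on the loss, allocation blind to unit.** Leaving unit out multiplies the variance of the difference by at most 1/(1 − r), and the standard error by 1/√(1 − r). Power is by normal approximation, before any loss of degrees of freedom.

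| r | SE ratio | Power, plain test | Power, unit removed |
|---|---|---|---|
| 0.01 | 1.005 | 80.0% | 80.4% |
| 0.05 | 1.026 | 80.0% | 82.0% |
| 0.10 | 1.054 | 80.0% | 84.0% |
| 0.20 | 1.118 | 80.0% | 87.9% |

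In patients: 1/0.95 = 1.053 and 1/0.90 = 1.111, so the plain test would need at most 70 × 0.053 = 3.7 or 70 × 0.111 = 7.8 more patients, about 4 to 8.

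**2. Why this is a bound.** Without stratification, arm and unit are not orthogonal, and each additional unit takes a degree of freedom. Simulation at r = 0.05 gave a variance ratio of about 1.04 with two units and 1.00 with four, not 1.053. At r = 0.10 it gave 1.09-1.10 and 1.06, not 1.111.

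**3. Power from adjustment alone, unstratified allocation (simulated, d = 0.67).** With unit effects drawn at random:

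- r = 0.05: 79.5% plain against 79.6% adjusted with two units; 79.7% against 79.1% with four. Over two to six units the change was about −1.5 to +0.5 points.
- r = 0.10: about +1 to +2 points. If two units differ by exactly a 10% share, the gain was about 3.
- r = 0.20: 83.8% against 87.3% with two units; 82.2% against 85.7% with four, so 3.5 points each.

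**4. Type I error, unstratified allocation.** The plain t-test rejected in 4.7% to 5.5% of runs under the null, which is nominal within simulation error.

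**5. Allocation balanced within unit, plain t-test.** With two units differing by an exact share of 5%, 10% or 20%, type I error was 0.044, 0.040 and 0.030 (60,000 runs). With random unit effects over two to six units it was about 0.040-0.048 at 5% and 0.037-0.046 at 10%. Four units at 20%: type I error 3.5% and power 82.7% for the plain test, against 5.1% and 86.6% with unit in the model. At 5-10%, adding the unit term gained about 0.5 to 2 points.

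**6. Chance imbalance.** Assume two units of 35 and allocation blind to unit. The count of intervention patients in one unit is hypergeometric (70, 35, 35): P(20:15 or worse) = 0.339 and P(21:14 or worse) = 0.151. With two equal units the gap between unit means is 2√r SD, so a 20:15 split shifts the observed difference by (5/35) × 2√r. That is 0.06 SD at r = 0.05 and 0.09 SD at r = 0.10, against a standard error of √(2/35) = 0.24 SD.

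**The case against.** The strongest reply is that the plan remains valid as written. With individual randomisation the plain test holds its level when allocation ignores unit, and errs on the safe side when allocation is balanced within unit. At a small unit share there is next to nothing to gain. Adjusting for the T0 score, which is collected but not used in the between-arm test, might absorb part of any stable unit difference. All of this stands, and it is why the point is minor.

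Three stronger readings are tempting, and the documents do not support them.

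- *Unit was ignored in the randomisation.* Section 6 gives only the ratio. That is silence, not a stated choice. Likewise, the open-ended list in Section 7 does not show that unit goes unrecorded, and a plural noun does not say how many units there are.
- *Unit imbalance could create or hide a massage effect.* In a single trial the estimate can shift, but randomisation makes this chance error, and the plain test's standard error already contains it. Counting it again as bias counts the same variance twice.
- *Whole units or shifts were allocated.* That would be a different and more serious problem. The protocol counts its sample and its arms in patients and nowhere mentions cluster allocation. Nor does it rule it out, which is a reason to state what was randomised.

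**Conclusion.** The point holds as a modest matter of efficiency and reporting; it does not invalidate the planned comparison. More than one unit takes part, the documents do not say that unit enters the allocation, and the between-arm test has no term for it. Assuming individual randomisation, the consequence is a small loss of precision or a slightly conservative test, depending on how patients were allocated.

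The size is negligible at a 1% unit share, roughly 0 to 2 points of power at 5-10%, and about 3 to 5 points at 20%. The equivalent of 4 to 8 patients is an upper bound for the unstratified case at 5-10%, and does not apply if allocation was stratified. These figures rest on an assumed unit share, an assumed reference of d = 0.67 with two-sided alpha 0.05, and two to six equal units. Severity: minor.

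**What to change.** - **Section 6:** state the number of units, and that individual patients are randomised 1:1, stratified by unit. If allocation is complete, report how it was actually done.
- **Section 7:** make unit an explicit field on the characteristics form.
- **Section 9:** replace the plain two-sample test by a linear model of the T2 score with arm, T0 score and unit as terms. If a rank test is kept, use the unit-stratified Wilcoxon (van Elteren) test.

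**Cost:** some wording, one field, and one degree of freedom per additional unit. With stratified allocation, the change brings no material loss even at a 0-1% share, and type I error returns to about nominal. If allocation was completed without stratification and there are many small units, the unit term may gain nothing or lose 1 to 3 points of power. The decision to include unit, and any rule for small units, should therefore be fixed before outcomes are examined. If enrolment is over, the analysis change alone remains possible, provided each patient's unit can be recovered.

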## 8. ETHICAL CONSIDERATIONS

- Ethical approval was obtained from the relevant institutional review board.
- Written informed consent was obtained from all participants prior to enrollment.

- Participation was voluntary, with the right to withdraw at any time without affecting their medical care.
- Confidentiality of participant data was strictly maintained (no names or identifiers are recorded in data collection tools).

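### T1 and T2 are tied to HRM session counts, with no calendar time for controls and no rule for HRM patients who miss or stop sessions

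*Combined protocol and SAP*

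**What the plan says.** Section 6 of the combined protocol and SAP gives one set of time points for the whole trial: "T0: Baseline (before the first session", "T1: Mid-intervention (after the 4th session" and "T2: Post-intervention (after the 8th session" (closing brackets omitted). The only sessions that section schedules are those of the HRM arm: "Received eight 21-minute HRM sessions over four weeks (two sessions per week) during routine hemodialysis, in addition to usual care". For the control arm it says: "Received usual care only (routine dialysis nursing care) without HRM".

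Section 2 uses the same anchor, asking about the effect "in patients receiving MHD compared to usual care after eight sessions". Section 5 also uses the word for dialysis, describing HRM as given to several reflex zones, the last being the heart: "and heart) during dialysis sessions".

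Section 9 compares the arms on their scores after the intervention, by t-test or Mann-Whitney test, and analyses T0, T1 and T2 within each group. On leaving the study, Section 8 says: "Participation was voluntary, with the right to withdraw at any time without affecting their medical care". No section gives a calendar date or window for the assessments, a control-arm equivalent of the session count, a rule for missed or stopped sessions, a missing-data method or an analysis population.

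**The concern.** A randomised comparison needs outcomes taken at the same time in both arms, on a schedule that does not depend on treatment received. Here the written schedule counts treatment sessions that only one arm has. Three things follow.

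- **Control timing is undefined.** Staff must decide when a control patient has reached T1 or T2. Two units could decide differently and both comply with the protocol.
- **HRM timing depends on adherence.** A patient whose missed session is made up reaches T2 late. A patient who stops HRM has, on the literal wording, no T2. Controls cannot lose their T2 in this way.
- **The moment of assessment is open.** The wording allows an assessment straight after a massage, and no matching moment is set for controls.

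At stake is the trial's main contrast. If those who stop HRM would have scored differently from those who continue, the T2 comparison sets completers in one arm against all available patients in the other.

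**Working it through.** **Inputs from Section 6.** Eight HRM sessions, four weeks, two per week; 35 patients per arm. Dialysis frequency, the share of patients who miss or stop HRM, and how they differ from the rest are not stated. Values for these below are assumptions.

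**1. The plan's own schedule.** 2 sessions per week × 4 weeks = 8 sessions, as stated. Session 4 falls at 4/2 = week 2.0 and session 8 at 8/2 = week 4.0. The schedule therefore implies times that could serve both arms, but the protocol does not make them the assessment rule.

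**2. If controls were timed by counting dialysis sessions.** The kth session falls at k divided by the weekly frequency.

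| Dialyses per week (assumed) | 4th session | 8th session | T2 gap from HRM week 4.0 |
|---|---|---|---|
| 2 | week 2.0 | week 4.0 | 0 |
| 3 | week 1.3 | week 2.7 | 1.3 weeks earlier |

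Under this reading the arms align only if dialysis is also twice weekly.

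**3. How often the HRM schedule might slip.** With an assumed independent miss probability m per session, the expected number of the 35 HRM patients receiving every planned session is 35 × (1 − m)^4 up to T1 and 35 × (1 − m)^8 up to T2.

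| m (assumed) | All of the first four | All eight |
|---|---|---|
| 2% | 32.3 | 29.8 |
| 5% | 28.5 | 23.2 |
| 10% | 23.0 | 15.1 |

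If missed sessions are made up, these patients reach T1 or T2 late. If not, the literal wording gives them no such time point.

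**4. Size of a completer selection, as illustration.** Let a share p of HRM patients never reach session 8, and let their mean differ by d SD from that of completers. The completer mean then departs from the mean of the whole arm by p × d.

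- p = 0.10, d = 0.5: 0.10 × 0.5 = 0.05 SD
- p = 0.20, d = 0.5: 0.20 × 0.5 = 0.10 SD

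The standard error of a difference in means with 35 per arm is √(2/35) = 0.239 SD. The shift is 0.05/0.239 = 0.21 to 0.10/0.239 = 0.42 of one standard error. It favours HRM if those who stop would have done worse, and works against HRM if they would have done better. The calculation assumes no such selection among controls.

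**The case against.** The strongest reply is that this is a gap in detail. Four weeks at two sessions per week gives weeks 2 and 4, and any sensible reader would assess controls then. That is a fair reading, and it limits the point: the control time points are unwritten, not meaningless. It does not remove the point. The rule on the page is a session count, and it parts from a week-4 rule as soon as a session is missed.

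A reader might infer more than the documents support:

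- **That the arms were measured at different times, or that patients who stopped HRM went unassessed.** The documents are silent on both. The wording permits these outcomes but does not establish them.
- **That both T1 and T2 exist only for patients who complete treatment.** T1 needs four of the eight sessions. Only T2 needs all eight.
- **That HRM patients were assessed immediately after a massage.** No interval is stated. The same visit, the next visit or the end of week 4 would all fit.
- **That the withdrawal clause shows one-sided loss.** It covers all participants, in both arms, and concerns leaving the study. It does not address stopping HRM while staying in the trial. Patients who withdraw would also be lost under calendar windows.

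It is also fair to say that the illustrated shift is modest, rests wholly on assumed inputs and could have either sign.

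**Conclusion.** The point holds in this form. T1 and T2 are anchored to HRM session counts, with no time or window for controls and no rule for missed or stopped sessions. T2, read literally, imposes a condition on the HRM arm alone. This is more than missing detail, because the written rule makes outcome timing depend on treatment received in one arm, and Section 9 then compares the arms at that time.

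The exposure is conditional. The timing gap at T2 ranges from none to about 1.3 weeks across the two assumed dialysis frequencies, and arises only if controls are timed by dialysis sessions. The selection shift is 0.05-0.10 SD, about 0.2-0.4 of a standard error, under assumed non-completion of 10-20% and an assumed 0.5 SD difference, with its direction unknown. These figures show what the wording leaves open. They are not estimates of bias in this trial.

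**What to change.** - Define T1 and T2 in both arms as the end of week 2 and the end of week 4 from T0, with the same window width and at the same point of the dialysis visit. T0 is itself written relative to the first session, so it needs a date set by the same rule in both arms.
- Assess every randomised patient who has not withdrawn from the study, whatever number of HRM sessions was received. Keep stopping HRM distinct from withdrawing from the study.
- Record the number of sessions delivered, and analyse patients as randomised.

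The protocol change is a few sentences and a table of windows, and the sample size does not change. The downside is that some HRM patients will be measured before completing eight sessions, which slightly dilutes the observed effect.

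Sections 6 and 8 are written partly in the past tense, although Section 9 looks forward. If data are already collected, windows cannot be imposed afterwards. The sponsor should then state the timing rule actually used for controls, report elapsed time from T0 and sessions received by arm, and analyse all assessed patients as randomised.

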## 7. STUDY INSTRUMENTS

1. Demographic and Clinical Characteristics Questionnaire (age, gender, education, income, duration of HD, etc.).
2. Arabic FACIT-Fatigue Scale (Version 4).
3. Arabic Beck Anxiety Inventory (Ar-BAI).

## 8. ETHICAL CONSIDERATIONS

- Ethical approval was obtained from the relevant institutional review board.
- Written informed consent was obtained from all participants prior to enrollment.

- Participation was voluntary, with the right to withdraw at any time without affecting their medical care.
- Confidentiality of participant data was strictly maintained (no names or identifiers are recorded in data collection tools).

## **9. STATISTICAL ANALYSIS PLAN**

- Normality Testing: Shapiro-Wilk test will be used to assess the normal distribution of continuous variables.
- Within-Group Comparisons: Parametric tests (e.g., Repeated Measures ANOVA) for normally distributed data, and non-parametric tests (e.g., Friedman test) for non-normal data across the three time points (T0, T1, T2).
- Between-Group Comparisons: Independent t-test or Mann-Whitney U test to compare post-intervention scores between the intervention and control groups.
- Multiple Comparisons: Bonferroni correction will be applied for post-hoc pairwise comparisons to control Type I error.
- Associations: Chi-square or Fisher's exact tests will be used to examine relationships between demographic/clinical characteristics and HRM effectiveness.
- Clinical Significance: Minimal Clinically Important Difference (MCID) will be calculated to determine the practical relevance of fatigue and anxiety score improvements. Analysis will be performed using SPSS.

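### The between-group test and its effect measure are not fixed in advance: the choice between a mean-based and a rank-based test is left until the data are seen

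*Combined protocol and SAP*

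**What the plan says.** All the relevant text is in section 9 (Statistical Analysis Plan) of the combined protocol and SAP.

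- Normality: "Shapiro-Wilk test will be used to assess the normal distribution of continuous variables". No significance level is given. Nor is it said whether the test is run per arm, on pooled scores, at each time point, or on residuals.
- Within groups, the result directs the choice: "Parametric tests (e.g., Repeated Measures ANOVA) for normally distributed data". Where the data fail the check, the plan turns to rank methods over T0 to T2 and gives Friedman's test as its example.
- Between groups: "Independent t-test or Mann-Whitney U test to compare post-intervention scores between the intervention and control groups". This sentence contains no rule for choosing.

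The section names no default test, no single effect measure, and no use of the T0 score in the between-group comparison. It does plan to judge improvements on both scales against an MCID. Section 2 asks how effective HRM is compared with usual care, so the between-group comparison is the one that answers the research question.

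**The concern.** A t-test compares means. Mann-Whitney compares rank ordering, that is, how often a patient in one arm scores above a patient in the other. These are different targets. The plan leaves open which one the trial will report, and this has three consequences.

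- The main analysis is not known before the data are seen.
- Fatigue and anxiety may be reported on different metrics although section 3 puts them in one hypothesis.
- Mann-Whitney alone gives no difference in scale points, and that is what the research question and a comparison with an MCID both need.

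Whichever test is chosen, the T0 score is collected but not used in the between-group comparison.

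**Working it through.** **Inputs from the documents.** Section 6: "70 adult patients receiving MHD (35 in the intervention group, 35 in the control group"). Section 5: FACIT-Fatigue runs 0-52 and Ar-BAI 0-63. Section 9: the tests listed above.

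**Assumptions, because the documents are silent.** Shapiro-Wilk at 0.05 in each arm; Mann-Whitney if either arm rejects, otherwise the t-test; outcome tests two-sided at 0.05; distribution shapes as in the table. A gamma distribution with shape k has skewness 2/√k, so k = 8, 4 and 2 give 0.71, 1.0 and 1.41. FACIT-like is normal with mean 28 and SD 10; BAI-like is gamma with mean 18 and SD 10; both are rounded and held to the scale range.

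**The plan's own figure.** The total of 70 comes without a calculation, so it cannot be reproduced. At 80% power, 35 per arm corresponds to a standardized difference of (1.960 + 0.842) × √(2/35) = 0.67. That value is used for power below.

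**Simulation, 10,000 trials per setting, 35 per arm** (all figures %; the first five result columns are with no effect):

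| Assumed shape | One arm rejects normality | Either arm rejects | Type I, t-test | Type I, Mann-Whitney | Type I, two-stage | Power at 0.67 SD, t / Mann-Whitney |
|---|---|---|---|---|---|---|
| Normal | 5.2 | 9.8 | 5.0 | 5.0 | 5.2 | 78.3 / 76.1 |
| FACIT-like | 3.8 | 7.7 | 5.4 | 5.1 | 5.4 | 78.1 / 76.2 |
| Gamma, skewness 0.7 | 28.6 | 49.6 | 4.7 | 4.8 | 5.1 | 79.2 / 80.4 |
| Gamma, skewness 1.0 | 52.0 | 76.6 | 5.5 | 5.5 | 5.9 | 79.2 / 83.9 |
| BAI-like | 61.0 | 85.2 | 5.2 | 4.8 | 5.2 | 79.3 / 84.8 |
| Gamma, skewness 1.4 | 82.9 | 97.0 | 4.6 | 4.9 | 5.0 | 79.3 / 89.6 |

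Monte Carlo standard error is about 0.2 points at 5% and 0.5 points at 50%.

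**Do two arms from the same population agree?** They disagree with probability 2p(1 − p). At skewness 0.7 this is 2 × 0.286 × 0.714 = 0.41; at skewness 1.0 it is 2 × 0.520 × 0.480 = 0.50. A further run of 5,000 trials gave rejection in 28% and 51% and disagreement in 41% and 48%.

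**Could the two outcomes go different ways?** If fatigue behaved like the FACIT-like row (7.7% sent to Mann-Whitney) and anxiety like the BAI-like row (85.2%), and the two selections were independent, the chance of different tests would be 0.077 × 0.148 + 0.923 × 0.852 = 0.80. Whatever their dependence, it is at least 0.852 − 0.077 = 0.775.

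**Does the unstated unit of testing matter?** At skewness 1.0 with a 0.67 SD difference, normality is rejected in 52% (one arm), 76% (either arm), 68% (pooled raw scores) or 83% (pooled residuals).

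**Does the choice change the verdict?** The t-test and Mann-Whitney fell on opposite sides of 0.05 in 2-3% of trials with no effect and in 5-12% at 0.67 SD.

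**Is the false-positive rate affected?** With the same distribution in both arms, the two-stage rule rejects in 5.0-5.9%. Among trials that pass the check, the t-test rejects more often under the more skewed shapes (6.7% at skewness 1.0, 7.3% BAI-like, 9.1% at skewness 1.4, the last from about 300 trials). These subsets shrink as skewness grows, and the overall rate remains about 5-6%.

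**The case against.** The best defence is that checking normality first is common practice and does little damage here. Much of it stands.

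- **False positives.** A reader might infer that the check materially inflates type I error. It does not when the arms share a distribution (5.0-5.9%).
- **Changes of shape.** A reader might also infer that the check creates false positives when HRM alters the distribution but not the mean. In equal-mean gamma settings where SD and skewness both differed (shape 4 v 2, and 4 v 1.5), the two-stage rule was significant in 9.2% and 13.8% of trials. Mann-Whitney fixed in advance gave 9.1% and 13.8%. The excess belongs to the rank test, which detects that the distributions differ; the check does not cause it. Changing skewness alone gave 5.1-5.7%.
- **The link is inferred.** Section 9 writes the normality rule only for the within-group tests. Saying that the plan makes Shapiro-Wilk choose the between-group test goes beyond the text, as does saying that it tests 35 patients per arm. But without that link, the plan leaves the choice entirely open.
- **Chance does not always dominate.** For near-normal or strongly skewed scores the selection is nearly settled. That applies to each outcome separately and does not keep both outcomes on one metric.
- **An estimate could still be given.** Section 9 plans an MCID assessment, and descriptive differences are not excluded. A Hodges-Lehmann shift could accompany Mann-Whitney, but the plan names none, and it is not a mean difference.

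**Conclusion.** The concern holds as one about pre-specification. The between-group test and the quantity it estimates are not fixed, may differ between fatigue and anxiety, and do not use T0 in either form. Under a per-arm check at 0.05, selection is largely a matter of chance at mild to moderate skewness (about 28-29% rejection at 0.7, 51-52% at 1.0) and close to determined outside that range. The documents give no score distributions, so which case applies is unknown. The level, the unit, the either-arm rule and every shape are assumptions. The documents and the calculations do not support a claim of materially inflated false-positive risk. The point merits correction before outcomes are compared by arm; it does not in itself invalidate the trial.

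**What to change.** In section 9, remove Shapiro-Wilk as the means of choosing tests. For both outcomes, prespecify one between-group analysis:

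- ANCOVA of the T2 score on randomized group and T0 score, or a mixed model over T0-T2 with the group difference at T2 as its target. Choose one now; leaving both open would repeat the problem.
- Report the adjusted mean difference in scale points with a 95% CI, using HC3 standard errors or a bootstrap for the ANCOVA. Set this estimate against the MCID.
- Check residuals descriptively, with no switch of method as a result.
- Report the rank test only as a named sensitivity analysis.

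The cost is SAP wording; robust and bootstrap intervals are available in SPSS, the package the plan names. Recruitment, visits and treatment are unaffected. The downside is some loss of power against a rank test if scores are very skewed: 79% against 90% at skewness 1.4 and a 0.67 SD difference, comparing an unadjusted t-test with Mann-Whitney. The ANCOVA itself was not simulated. How much adjustment for T0 would recover depends on the T0-T2 correlation, which the documents do not give.

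### The three time points are analysed only within arms, the one between-arm test ignores baseline, and no analysis is primary, so an HRM-only within-arm result could be reported as the effect

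*Combined protocol and SAP*

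**What the plan says.** Section 6 describes a "Two-group parallel Randomized Controlled Trial (RCT) with a 1:1 allocation ratio" with "70 adult patients receiving MHD (35 in the intervention group, 35 in the control group"). Scores are collected at baseline (T0), after the fourth session (T1) and after the eighth; the last is defined as "T2: Post-intervention (after the 8th session").

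The question and hypothesis are between-arm. Section 2 asks "How effective is HRM in reducing fatigue and anxiety levels in patients receiving MHD compared to usual care after eight sessions". Section 3 states: "There is a statistically significant difference in fatigue and anxiety levels between hemodialysis patients receiving HRM plus usual care and those receiving usual care alone". Section 4 includes two relevant objectives. The second, "Evaluate the effect of the HRM program on fatigue and anxiety post-intervention", names no comparator. The third is "Compare post-intervention changes between the intervention and control groups".

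Section 9 gives the analysis of T0, T1 and T2 as "Within-Group Comparisons: Parametric tests (e.g., Repeated Measures ANOVA) for normally distributed data, and non-parametric tests (e.g., Friedman test) for non-normal data". A separate line gives an independent t-test or Mann-Whitney U test of scores after the intervention, HRM against control. Bonferroni correction is tied to post-hoc pairwise comparisons. Section 9 contains no group factor in the repeated-measures analysis, no group-by-time term, no change score, no baseline adjustment and no designation of a primary analysis.

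**The concern.** A change over time within one arm is not an estimate of the HRM effect. It also contains any time trend, any regression to the mean and any effect of completing the same questionnaires three times. The control arm exists to remove these, and only a between-arm contrast does so. Finding one arm significant and the other not does not test the difference between them, and its error rate is not controlled.

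Two gaps in Section 9 leave room for that reading. First, the three-time-point data are analysed only under the within-group line, and no sentence says which result decides efficacy. Second, the third objective promises a comparison of changes, but the between-arm test compares scores at one time point without baseline. A report could lead with the within-arm results and still be consistent with the plan.

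**Working it through.** **Inputs from the documents.** Two arms, 1:1, 35 per arm; T0, T1 and T2; the tests listed in Section 9.

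**Assumptions, because the documents give none.** Two-sided alpha 0.05, SD 1 at each time, normal data, equal correlation ρ between time points (0.5 to 0.7), no dropout, T1 change half the T2 change.

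**The plan's own figure.** The total of 70 comes without alpha, power, effect size or SD, so it cannot be reproduced. For orientation, 35 per arm detects (1.960 + 0.842) × √(2/35) = 0.67 SD with 80% power in an unadjusted comparison at T2.

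**Step 1: how often HRM alone is significant when there is no HRM effect.** Give both arms the same change δ from T0 to T2, with means 0, δ/2, δ. The squared deviations of these means sum to δ²/2, so each arm's repeated-measures F test (2 and 68 degrees of freedom) has noncentrality

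λ = 35 × (δ²/2) / (1 − ρ) = 17.5 δ² / (1 − ρ).

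Let p be that test's chance of significance. The arms are independent, so P(HRM significant, control not) = p(1 − p), which cannot exceed 25%. Example: ρ = 0.5 and δ = 0.4 give λ = 17.5 × 0.16 / 0.5 = 5.6, p = 0.53 and p(1 − p) = 0.25.

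**Step 2: simulation of the whole plan** (20,000 trials per setting, same change in both arms).

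| ρ | δ (SD) | HRM alone significant | of which T2 t-test not significant | T2 t-test false positive |
|---|---|---|---|---|
| 0.5 | 0.2 | 13.2% | 12.2 points | 5.1% |
| 0.5 | 0.3 | 21.8% | 20.4 points | 5.0% |
| 0.5 | 0.4 | 24.7% | 23.1 points | 4.9% |
| 0.5 | 0.5 | 19.4% | 18.2 points | 4.9% |
| 0.7 | 0.2 | 18.8% | 17.6 points | 5.1% |
| 0.7 | 0.3 | 25.2% | 23.7 points | 5.0% |
| 0.7 | 0.4 | 17.6% | 16.6 points | 4.9% |
| 0.7 | 0.5 | 6.6% | 6.2 points | 5.0% |

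The simulated values match p(1 − p) within simulation error. With no change in either arm, the HRM-only pattern occurs in 4.9% of trials. In 92% to 94% of the HRM-only trials the planned T2 test is not significant (12.2/13.2 = 92%; 23.1/24.7 = 94%). A group-by-time test is also falsely positive in about 5% throughout.

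**Step 3: what baseline adjustment gains.** For a true effect of 0.5 SD at T2, the noncentrality of the between-arm t statistic is 0.5 × √(35/2) / f, where f = 1 without adjustment and f = √(1 − ρ²) with T0 as covariate.

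- Unadjusted: 2.09, power 54%.
- ANCOVA, ρ = 0.5: f = 0.866, noncentrality 2.42, power 66%.
- ANCOVA, ρ = 0.7: f = 0.714, noncentrality 2.93, power 82%.

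The omnibus group-by-time F test has simulated power of 45% (ρ = 0.5) and 66% (ρ = 0.7). It is below the ANCOVA in both cases, and below the unadjusted T2 test in the first.

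**The case against.** The strongest reply is that the plan already holds a valid test of its question. Section 2 asks about HRM against usual care after eight sessions, T2 is that time point, and a randomised comparison of T2 scores answers it with the right error rate. A group-by-time term is not required for validity. This stands, and it rules out several stronger readings.

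- *That the plan has no between-arm test of efficacy.* It has one.
- *That the second objective is assigned to the within-arm tests.* No sentence does so. That objective names no comparator, but it refers to the time after the intervention, as the between-arm line does.
- *That the false-claim risk is near one half.* At ρ = 0.6 and a common change of 0.3 SD, exactly one arm is significant in about 47% of trials. About half of those are control-only results, which nobody would report as a benefit; HRM-only is about 24%.
- *That leaving T1 out of the between-arm test is an error.* T1 is a mid-course measurement and the question concerns eight sessions.

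The reply can also say that the repeated-measures ANOVA is given as an example and might be run with arm as a factor. The within-group label does not say so, and the Friedman alternative cannot test an interaction.

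Finally, a false claim would nearly always mean setting aside the plan's own non-significant T2 result. That is true, but the plan has no rule against doing so.

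**Conclusion.** The point holds as a gap in hierarchy and alignment, and it should be fixed. It does not invalidate the trial. The three-time-point data are analysed only within arms, the between-arm test discards baseline and does not compare changes as the third objective requires, and no analysis is primary.

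Under an equal change in both arms, an HRM-only within-arm result arises in about 7% to 25% of trials, against about 5% for the planned T2 test. The range rests on assumed SD, correlation, alpha and time trend. The curve is hump-shaped: it peaks near 25% and falls again when the shared change is large. The Friedman and Mann-Whitney branches were not simulated, but the argument against comparing two within-arm p-values is the same.

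A reader might infer that efficacy will be judged from the within-arm tests. The documents do not say so; they only fail to exclude it.

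**What to change.** For each outcome (FACIT-Fatigue and Ar-BAI), name as primary the between-arm difference at T2 adjusted for T0, with its 95% CI. Either of these will do:

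- ANCOVA of T2 on arm and T0.
- A mixed model of T1 and T2 with arm, time, arm-by-time, T0 and T0-by-time, reading off the T2 contrast. If T0 is instead modelled as an outcome with a common mean in both arms, drop the arm main effect, since keeping it alongside the full interaction lets the T0 means differ.

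Report the T1 between-arm contrast as secondary. Do not rest the conclusion on the omnibus group-by-time F test. State that within-arm changes are descriptive (mean change, 95% CI) and carry no efficacy claim.

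The cost is SAP wording and a standard procedure in SPSS, the software already named. No new data are needed. The downside is that within-arm p-values can no longer be quoted as evidence of effect.
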